8.12.4 Vital Signs

Vital signs will be collected at Day 1 pre-surgery (Arm 1)/pre-dose (Arm 2 and re-treatment), Day 1 between 1-30 minutes post-dose and Day 8 (Arm 2 and re-treatment). Summary tables of the actual values and change from baseline for each vital sign will be provided by scheduled visit. Summaries will include data from scheduled assessments only, and all data will be reported according to the nominal visit date for which it was recorded (i.e., no visit windows will be applied).

8.12.5 Electrocardiogram Parameters

Electrocardiogram (ECG) parameters (rhythm, ventricular rate, PR interval, QRS duration, QT interval and QTcF interval) will be collected pre-dose, between 1-30 minutes post-dose and Day 8 and will be summarized with descriptive statistics of the change from baseline value by time point for Arm 2 and re-treatment arm. Overall ECG result (normal or abnormal) will be summarized by time point. Summaries will include data from scheduled assessments only, and all data will be reported according to the nominal visit for which it was recorded (i.e., no visit windows will be applied).

Confidential Page 31 of 37

8.12.6 Prior and Concomitant Medications

All medications will be coded using the latest version of the World Health Organization (WHO) Drug coding dictionary. The actual dictionary versions used will be presented in the CSR.

Concomitant medications will be summarized by standardized medication name and treatment arm for the safety analysis population. Subject incidence will be presented. Subjects who take the same medication (in terms of the standardized medication name) more than once will only be counted once for that medication.

[figure not shown]
Prior medications are those medications that were stopped before the first neurosurgery date for Arm 1 or the first dose date for Arm 2. Concomitant medications are medications taken at least once on or after the first neurosurgery date for Arm 1 or the first dose date for Arm 2.

If partial dates exist for concomitant medication, the start dates will be imputed to the first of the month (for missing day) or first of the year (for missing day and month) for purposes of assigning the medication to a prior or concomitant medication.

Prior medications will be listed only. Prior and concomitant medications will be listed separately, including derived study day.

8.12.7 Physical Examination

Physical examination will be listed for the safety analysis population.

Confidential Page 32 of 37

Confidential Page 33 of 37

13 APPENDICES

13.1 Calculation of 95% Confidence Interval for Ratio of Paired Percentages

The 95% CI for the ratio of paired percentages (sensitivity and specificity) will be calculated using Pepe's formula (Pepe, 2003) as follows.

The paired data of sensitivity between tozuleristide and surgical designation can be summarized in a 2×2 table of all tumor-positive biopsies by central pathology:

		Surgical Designation	
		Tumor*	Not Tumor*
Tozuleristide	Positive*	a	ь
Fluorescence	Negative*	c	d

*See Section 4.1

The paired data of specificity between tozuleristide and surgical designation can be summarized in a 2×2 table of all tumor-negative biopsies by central pathology:

		Surgical Designation	
		Tumor*	Not Tumor*
Tozuleristide	Positive*	e	f
Fluorescence	Negative*	g	h

^{*}See Section 4.1

[figure not shown]

Confidential Page 34 of 37

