4 STUDY ENDPOINTS

4.1 Primary Efficacy Endpoints

[figure not shown]
The primary efficacy endpoints are:

- 1. Ratio of sensitivity of tozuleristide fluorescence in equivocal tissue biopsies from subjects with fluorescence-positive tumors compared to the sensitivity of surgical designation from the same biopsies under white light conditions
- 2. Ratio of specificity of tozuleristide fluorescence in equivocal tissue biopsies from subjects with fluorescence-positive tumors compared to the specificity of surgical designation from the same biopsies under white light conditions
- 3. Sensitivity of tozuleristide fluorescence to detect tumor in equivocal tissue biopsies from subjects with fluorescence-positive tumor
- 4. Specificity of tozuleristide fluorescence to detect tumor in equivocal tissue biopsies from subjects with fluorescence-positive tumor

Fluorescence positivity for the primary endpoints is defined as weak or strong fluorescence as determined by the imaging operator fluorescence assessment based on displayed fluorescence signal and exposure setting.

Confidential Page 11 of 37

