8.11.1 Primary Efficacy Endpoints

8.11.1.1 Primary Analyses of Sensitivity and Specificity

The primary efficacy analyses will be based on Group 2 in the full analysis population (Section 7). Each of the 4 sets of statistical hypotheses will be tested at two-sided 5% level (Section 5) using the repeated measures log-linear model specified in this section. Each equivocal tissue specimen from Group 2 that is determined to be either tumor positive or tumor negative by central pathology, and has an image operator assessment and/or a surgeon assessment will be used in the analysis.

[figure not shown]
Confidential Page 22 of 37

[figure not shown]
Confidential Page 23 of 37

[figure not shown]
Confidential Page 24 of 37

Confidential Page 25 of 37

Confidential Page 26 of 37

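### SAP 13.1 builds the 95% CI for the sensitivity and specificity ratios on pooled biopsy tables, while 8.11.1.1 tests those ratios with a repeated measures model on a wider specimen set; the plan should tie interval and test together (minor)

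*SAP*

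**What the plan says.** **Interval.** SAP 13.1 says, without condition: "The 95% CI for the ratio of paired percentages (sensitivity and specificity) will be calculated using" a named formula. The sensitivity data are set out in a 2×2 "table of all tumor-positive biopsies by central pathology" (cells a to d) and the specificity data in a 2×2 "table of all tumor-negative biopsies by central pathology" (cells e to h). Each table crosses fluorescence with surgical designation. The counting unit is the biopsy, and no subject index is visible. The category labels carry a footnote, "See Section 4.1".

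**Test.** SAP 8.11.1.1 says that each of the four sets of primary hypotheses will be "tested at two-sided 5% level (Section 5) using the repeated measures log-linear model specified in this section". A Group 2 equivocal specimen that central pathology calls positive or negative, and that "has an image operator assessment and/or a surgeon assessment will be used in the analysis", enters.

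**Endpoints.** SAP 4.1 defines endpoint 1 as fluorescence sensitivity "compared to the sensitivity of surgical designation from the same biopsies under white light conditions", and endpoint 2 as fluorescence specificity "compared to the specificity of surgical designation from the same biopsies under white light conditions".

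**Missing readings.** SAP 8.3 rules out imputation.

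The 13.1 formula, the rest of 8.11.1.1, the Section 5 hypotheses and the 13.3 code are not shown in the public text.

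**The concern.** Two mismatches are visible.

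**Method.** The test allows for repeated measures, whereas the interval is set out on pooled biopsy counts. Protocol 2.5.1 expects more than one area of equivocal tissue in a long resection, so several biopsies per subject are plausible. A formula using only table cells treats them as independent.

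**Specimens.** A paired table needs both readings on each biopsy. The and/or rule admits specimens with one. Operator-only specimens have an evident purpose, because endpoints 3 and 4 need only the operator's reading. A surgeon-only specimen can contribute only to a ratio, and there it departs from the same-biopsy definition.

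The test itself is not at stake. The stake is the interval for endpoints 1 and 2, from which readers will judge how far fluorescence improves on the surgeon. It could cover less than 95%, rest on a different estimate from the test, or include 1 when the test rejects equality (or the reverse).

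**Working it through.** The public documents give no worked interval, specimen count per subject, correlation or assumed accuracy, so there is no plan figure to reproduce. Every input below is an assumption except the 95% level and the table layout.

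**1. What a cell-only interval contains.** The SAP formula is not shown, so I use the standard delta-method variance for a paired ratio:

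- Sensitivity: ratio = (a+b)/(a+c); SE of log ratio = √[(b+c)/((a+b)(a+c))].
- Specificity: ratio = (g+h)/(f+h); SE = √[(f+g)/((g+h)(f+h))].

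For each biopsy let D = F/pF − S/pS, with F and S the two correct-call indicators and pF and pS their rates. The cell formula adds up the variance of D over biopsies as if they were independent. With m biopsies of one pathology class per subject, the variance should be multiplied by 1+(m−1)ρ, where ρ is the within-subject correlation of D. So nothing is lost when m = 1. Little is lost when a subject's effect moves both readings alike, because it cancels in D. The interval is too narrow when m exceeds 1 and the contrast itself varies between subjects.

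**2. Illustration with invented counts** (a=70, b=25, c=10, d=5).

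- Ratio 95/80 = 1.19; SE = √(35/(95×80)) = 0.0679; CI = exp(0.1719 ± 0.1330) = 1.04 to 1.36.
- If clustering doubles the variance, SE = 0.0960 and the CI is 0.98 to 1.43. The change comes once the variance multiplier passes (0.1719/0.1330)² = 1.67.
- Add 10 operator-only specimens (5 positive) and 10 surgeon-only specimens (9 called tumor). The all-readings ratio is (100/120)/(89/120) = 1.12; the table ratio stays at 1.19.

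**3. Coverage of the cell-only interval by simulation.** 80 subjects; both sensitivities 0.75; biopsies per subject 1+Poisson; subject-level beta probabilities for the two readings, linked by a Gaussian copula with latent correlation 0, 0.5, 0.8 or 1; 4,000 replicates per case (Monte Carlo SE √(0.95×0.05/4000) = 0.003).

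| Mean biopsies | Within-subject correlation, fluorescence/surgeon | Separate (0) | Half (0.5) | Largely shared (0.8) | Fully shared (1) |
|---|---|---|---|---|---|
| 1.3 | 0.2/0.1 | 0.941 | 0.943 | 0.948 | 0.950 |
| 1.3 | 0.4/0.2 | 0.925 | 0.934 | 0.946 | 0.946 |
| 1.3 | 0.6/0.4 | 0.916 | 0.929 | 0.933 | 0.947 |
| 2 | 0.2/0.1 | 0.925 | 0.932 | 0.939 | 0.952 |
| 2 | 0.4/0.2 | 0.895 | 0.919 | 0.926 | 0.942 |
| 2 | 0.6/0.4 | 0.864 | 0.892 | 0.914 | 0.944 |
| 3 | 0.2/0.1 | 0.897 | 0.927 | 0.939 | 0.945 |
| 3 | 0.4/0.2 | 0.841 | 0.876 | 0.917 | 0.944 |
| 3 | 0.6/0.4 | 0.797 | 0.835 | 0.884 | 0.942 |

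With one biopsy per subject or zero correlation, coverage is 0.94 to 0.96. A subject-clustered sandwich interval for the same log ratio covers 0.942 to 0.959 in all 80-subject cases. For specificity (30 or 50 subjects, mean two tumor-negative biopsies, both specificities 0.60 or 0.75, correlations 0.2/0.1 and 0.4/0.2), the cell-only interval covers 0.90 to 0.94 with separate or half-shared effects, 0.93 to 0.95 with largely shared and 0.94 to 0.96 with fully shared effects.

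Taking the null ratio as 1, the cell-only and clustered intervals disagree on excluding 1, at two biopsies, in 2–9% of trials (separate or half shared), 2–4% (largely shared) and 1–2% (fully shared or no correlation). The last figure is background noise between two variance estimators.

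**4. Specimen set alone.** 80 subjects, mean two biopsies, correlations 0.4/0.2, half-shared effects, true ratio 1.00 or 1.13, clustered variance for both analyses. The comparison is both-readings specimens against all available readings.

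| Single-reading share | Mean difference in ratio | Disagree on excluding 1 | Difference if those specimens are harder (sensitivity 0.2 lower) | Disagree |
|---|---|---|---|---|
| 2% | 0.004–0.006 | 1–4% | 0.007–0.008 | 1–5% |
| 5% | 0.007–0.009 | 2–6% | 0.015–0.017 | 3–10% |
| 10% | 0.010–0.014 | 2–8% | 0.027–0.033 | 5–16% |

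**5. Direction.** A separately built simulation (latent correlation 0 to 0.6, the two readings independent given pathology, 2,000 runs per setting) gives a clustered-to-cell-only SE ratio of 1.08 to 1.33 with clustering alone. With 10–20% single readings and no clustering the ratio is 0.94 to 0.98: the table then drops information the model keeps, and its interval is slightly the wider of the two.

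**The case against.** The strongest reply is that the deciding text is not public. Material missing from the extract is not missing from the plan: the formula may adjust for clustering, and 8.11.1.1 may already take the interval from the model. A log-linear model yields its own interval for a ratio, and 13.1 may serve a supportive analysis. This stands, and it is why the point is conditional.

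A reader might infer from the footnote that 13.1 is the designated interval for endpoints 1 and 2. The documents do not support that. The asterisks sit on the category labels, and 4.1 is where fluorescence positivity is defined, so the footnote reads most naturally as a pointer to definitions. No visible sentence in 8.11.1.1 calls on 13.1.

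The and/or wording can also be defended as one inclusion rule for four hypotheses, and using all available readings in a repeated measures model is legitimate. Surgeon-only specimens may be rare or absent. The workflow in the Protocol abstract has both people recording the same region, and the full analysis population requires operator assessment. That requirement is worded by subject, however, and does not clearly exclude a surgeon-only specimen. The 2–10% shares above have no source in the documents.

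None of this removes the plain-text difference between the and/or rule and the same-biopsy definition, or the absence of a visible statement of which interval goes with the test.

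**Conclusion.** The point holds as a minor, conditional one. On the visible text, interval and test for the ratio endpoints differ in method and in specimens. **If** 13.1 supplies the interval reported for endpoints 1 and 2, **and** its formula uses only table cells, that interval ignores within-subject correlation. It is then too narrow when subjects contribute several biopsies of one pathology class and the fluorescence-versus-surgeon contrast varies between subjects.

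Its size cannot be set from the documents. At an average of two biopsies, coverage runs from 0.86 to about nominal, depending on assumed correlation and sharing; with one biopsy per subject or a fully shared effect the loss is negligible. Disagreement rates further assume a null ratio of 1, which is plausible for a two-sided test of equality but not visible in Section 5.

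Two stronger readings should be resisted. One is that the primary test is invalid: the model is the visible decision rule, and nothing here impugns it. The other is that the table interval is always too narrow: omitting single readings can make it slightly wider than the model's. Confidence is medium.

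**What to change.** - Report the 95% CI for endpoints 1 and 2 from the repeated measures log-linear model used for the test, as the exponentiated fluorescence-versus-surgeon contrast. State that the variance is clustered by subject; the visible text does not say whether the repeated unit is the subject or the specimen.
- Name one specimen set for the two ratios. Specimens with both readings would match 4.1; all available readings can be a sensitivity analysis. Endpoints 3 and 4 keep every specimen with an operator reading.
- Label the 13.1 tables, and any interval from them, as supportive.
- If few subjects contribute to specificity, add a small-sample correction or a subject-level bootstrap. The uncorrected clustered interval covered 0.941 to 0.952 at 30 subjects, so the gain would be small.

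The cost is SAP wording and a few lines of code. Section 13.3 already plans sample code for the model, SAP Section 1 allows amendment before database lock, and no new data are needed. The downsides are a possibly wider interval and the loss of any single-reading specimens from the ratios. If the text not shown already does this, the sponsor need only confirm it.

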13.2 Definition of Tumor Diagnosis

Subjects are eligible for enrollment based on MRI evidence consistent with a pediatric primary CNS tumor. Study specimens are subjected to pathological analysis and along with local pathology assessments, a diagnosis is assigned by Central Pathology. Tumor diagnosis is based on WHO Classification of Tumors of the Central Nervous System, 4th Edition, 2016. Subjects with ambiguous pathological diagnosis of tumor or no definitive pathological diagnosis are considered to have a pediatric primary CNS tumor. Subjects with a pathological diagnosis indicative of non-tumorous abnormality are considered to not have a pediatric primary CNS tumor.

[figure not shown]
13.3 Sample SAS Code for Repeated Measures Log-Linear Regression

Confidential Page 35 of 37

Confidential Page 36 of 37

Confidential Page 37 of 37
